## 6.1 CRITERIA FOR SUBJECT ELIGIBILITY

### 6.2 Subject Inclusion Criteria

1. Recurrent and/or metastatic HPV-related carcinoma of the cervix, anus, vagina, vulva, penis, or oropharynx. The cancer diagnosis must be confirmed by slide review in the MSKCC Department of Pathology. HPV positive status must be demonstrated by HPV in situ-hybridization (ISH) and/or by p16 immunohistochemistry (IHC).  
Note: For cervix squamous cancer, HPV ISH test or p16 IHC test is not required, because all cervix squamous cancers are presumed to be HPV-associated.
2. Adults ( $\geq$  18 years of age)
3. ECOG performance status of 1 or better
4. Measurable disease according to RECIST 1.1 criteria
5. Availability of archived tumor tissue for correlative studies (5 unstained slides)
6. Adequate organ function, as follows:
  - Adequate bone marrow reserve: absolute neutrophil count (ANC)  $\geq$  1.5  $\times$  10^9/L, platelets  $\geq$  160  $\times$  10^9/L, hemoglobin  $\geq$  10 g/dL
  - Hepatic: total bilirubin within ULN (upper limit of normal); alkaline phosphatase (AP), aspartate transaminase (AST) and alanine transaminase (ALT)  $\leq$  2.0  $\times$  ULN
  - Renal: Serum creatinine  $\leq$  1.3 mg/dL. Patients with serum creatinine  $>$  1.3 mg/dL may be eligible if creatinine clearance (CrCl)  $\geq$  55 mL/min based on the standard Cockroft and Gault formula.
7. Ability to swallow oral medication.
8. Patients of childbearing potential must have a negative serum pregnancy test within 14 days of treatment. Patients must agree to use a reliable method of birth control during and for 6 months following the last dose of study drug.
9. At least one prior systemic therapy regimen for R/M HPV-related carcinoma

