## 8.1 PRETREATMENT EVALUATION

- Complete medical history including current medications, physical examination including evaluation of ECOG performance status within 14 days prior to therapy.
- Pathology review at MSKCC
- The following laboratory studies will be obtained within 14 days prior to therapy:  
Complete blood count with white blood cell differential and platelet counts;  
Comprehensive profile (including electrolytes, bicarbonate, blood urea nitrogen (BUN), creatinine, glucose, alkaline phosphatase, aspartate aminotransferase (AST), alanine aminotransferase (ALT), total bilirubin, total protein, albumin, and glucose); prothrombin time and activated partial thromboplastin time
- Serum pregnancy test for women of childbearing potential within 14 days prior to therapy.
- Electrocardiogram within 8 weeks prior to therapy
- Baseline cross-sectional imaging of the known sites of disease (CT or MR) within 4 weeks prior to therapy

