## 9.0 TREATMENT/INTERVENTION PLAN

### 9.1 Clinical Plan

Study subjects will self-administer ribavirin 1400 mg PO BID (total dose, 2800 mg/day).

Ribavirin should be taken with food, not in a fasting condition.

All patients will complete pill diaries to document administration of study drug. Patients should be instructed to bring completed pill diaries and all pill bottles to each visit.

Cycle length is 28 days with continuous dosing. Clinic visits for safety assessments and routine laboratory studies will occur weekly in Cycle 1, in weeks 1 and 3 of Cycle 2, and on Week 1 of subsequent cycles ( $\pm$  3 days). Although clinic visits and lab tests should generally occur on the same day each week to facilitate continuity with providers, there is no requirement regarding the day of the week of these visits.

Toxicities will be graded according to NCI CTCAE version 4.

Cross sectional imaging (CT or MRI) is obtained at baseline and q2 cycles. Imaging scans will be scheduled to occur in the last week ( $\pm$  2 days) of each even-numbered cycle. However, after completion of cycle 4, the interval between scans may be increased to q3 cycles, at the discretion of the investigator.

Response assessments will follow RECIST 1.1 criteria (See Section 12).

Patients may remain on study until disease progression or unacceptable toxicity. There will be a post-treatment visit 30 days ( $\pm$  7 days) from last dose of drug for patients who maintain active follow up. If a patient is unable to attend the post-treatment visit due to medical or logistical issues or lost to follow-up, this will not be a protocol violation.

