## 10.0 EVALUATION DURING TREATMENT/INTERVENTION.

		Cycle 1	Cycle 2	Cycle ≥3	Post Treatment d
	Baseline	Weeks 1, 2, 3 and 4	Weeks 1 and 3	Week 1	
History and Physical	X	X	X	X	X
CBC, Comp panel	X	X	X	X	X
PT/aPTT	X				
Serum Pregnancy Test	X				
EKG a	X				
Radiologic Assessment (CT or MRI) b	X		X	X	
Archival Tissue	X				
Research biopsy c					X c
Adverse Event and Concomitant Medications Monitoring		Continuous Monitoring for Adverse Events			
Ribavirin		Continuous BID dosing			

a Baseline EKGs to be performed within 8 weeks prior to treatment

b Radiologic assessments occur at baseline (within 4 weeks of starting treatment) and q2 cycles. Imaging scans will be scheduled to occur in the last week ( $\pm$  2 days) of each even-numbered cycle. However, after completion of cycle 4, the interval between scans may be increased to q3 cycles, at the discretion of the investigator.

c Research biopsy at time of progression of disease is only for patients who experience initial radiographic response. When done, every effort should be made to obtain the research biopsy within 2 weeks of the last dose of ribavirin.

d The post treatment evaluation should occur 30 days ( $\pm$  1 week) after the last dose of ribavirin, for patients who maintain active follow up. The one exception is the post-treatment biopsy for patients who had previously responded (see footnote b)

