## 11.1 TOXICITIES/SIDE EFFECTS

### 11.2 General Considerations

#### Ribavirin Toxicities:

Hematologic: anemia, thrombocytopenia, leukopenia, lymphopenia

Gastrointestinal: anorexia, nausea, diarrhea

Hepatic: elevated liver function tests

Pulmonary: dyspnea, cough

Reproductive: may be teratogen

Constitutional: fatigue, musculoskeletal pain

Dermatologic: alopecia, pruritus, rash

Neurologic: headache, dizziness

Endocrine and metabolic: hyperuricemia

The listed ribavirin toxicities include those side effects described in the treatment of hepatitis C in which ribavirin may be given in combination with peginterferon alfa [13-16], and those side effects described in other settings including oncology research in which ribavirin was given at doses up to 1400 mg po BID [37][17, 21].

Even when the patient meets criteria for continued treatment at full dose per the protocol, the investigator retains the discretion to delay the next treatment and/or reduce ribavirin dose if there are safety concerns and/or logistical issues. Any dose reductions not specified in the protocol should be discussed with the principal investigator.

Doses that have been reduced for toxicity must not be re-escalated.

Treatment delays of up to 21 total days per cycle are allowed in a given cycle. Any patient who requires a treatment delay of >21 days, for medical and/or logistical reasons, in a given cycle should be removed from study.

If an investigator feels that a patient requires a dose reduction and/or dose delay other than those specified herein, this may be allowed after communication with the Principal Investigator, and would not be considered protocol violation. If the Principal Investigator is unavailable, Co-PI or designated covering investigator may address such issues as they arise.

Dose modification guidelines in this section are only for those adverse events thought to be at least possibly related to ribavirin.

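### The only scheduled pregnancy test is at baseline, although a possible teratogen is then dosed continuously with no fixed end; repeat tests on blood already drawn would be a cheap safeguard

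*Combined protocol and SAP*

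**What the plan says.** **Entry and contraception.** Section 6.2, item 8, sets two conditions: "Patients of childbearing potential must have a negative serum pregnancy test within 14 days of treatment" and "Patients must agree to use a reliable method of birth control during and for 6 months following the last dose of study drug".

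**Timing of the test.** Section 8.1 repeats the first condition: "Serum pregnancy test for women of childbearing potential within 14 days prior to therapy". In the Section 10.0 calendar the pregnancy test row has one mark, at baseline. The cycle columns and the post-treatment column carry history, physical examination, blood count and chemistry panel, but no pregnancy test.

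**Exposure.** Section 9.1 prescribes continuous dosing in 28-day cycles and sets no maximum: "Patients may remain on study until disease progression or unacceptable toxicity". Section 11.2 includes in its toxicity list "Reproductive: may be teratogen".

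**Blood draws.** Section 9.1 says "Clinic visits for safety assessments and routine laboratory studies will occur weekly in Cycle 1, in weeks 1 and 3 of Cycle 2", and then in week 1 of each later cycle. A post-treatment visit follows 30 days "after the last dose of ribavirin, for patients who maintain active follow up" (Section 10.0, footnote d). Section 9.1 excuses a missed visit: for a patient "unable to attend the post-treatment visit due to medical or logistical issues or lost to follow-up, this will not be a protocol violation".

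**What happens if a pregnancy occurs.** Section 13.0 does not list pregnancy among the reasons for removal. It does allow removal for unacceptable toxicity, for non-compliance, or when the study doctor judges it to be in the patient's interest. Section 11.2 lets the investigator delay or reduce dosing over safety concerns. Section 17.3 counts a birth defect as serious and requires possibly related events to be reported even after the 30-day period, but does not make pregnancy itself reportable.

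**The concern.** The protocol treats fetal exposure as a real hazard: it screens for pregnancy at entry and asks for contraception well beyond the last dose. After entry, however, protection rests on contraception alone, with no scheduled check on whether it has worked. If it fails between the screening test and day 1, or in a later cycle, detection depends on history, examination and adverse event monitoring. The patient could go on taking the drug until the pregnancy is noticed clinically.

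What is at stake is the length of an avoidable fetal exposure. Sample size, error rates and the efficacy analysis are unaffected.

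**Working it through.** The plan gives no figure of its own on this point, so there is none to reproduce. The check is a count of days, blood draws and tests on the stated schedule.

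**Inputs.** Earliest permitted test: 14 days before therapy (Sections 6.2 and 8.1). Cycle length: 28 days (Section 9.1). Post-treatment visit: 30 days after the last dose, plus or minus 7 (Sections 9.1 and 10.0). Treatment visit window: plus or minus 3 days (Section 9.1). Multiple-dose half-life: 274 to 296 hours (Section 5.0, Pharmacology). The number of cycles, k, is not fixed by the plan; k = 2 and k = 6 are used as illustrations.

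**1. Days from the only test to the 30-day visit**, with treatment ending at the end of cycle k and no delays: 14 + 28k + 30.

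**2. Scheduled blood draws from Cycle 1 week 1 onward**, for k of 2 or more: 4 in Cycle 1, 2 in Cycle 2, one in each later cycle and one post-treatment, so 4 + 2 + (k − 2) + 1 = k + 5.

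**3. Tests the fix would add**: one per cycle and one post-treatment, so k + 1.

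| | k = 2 | k = 6 |
|---|---|---|
| Days from only test to 30-day visit | 14 + 56 + 30 = 100 | 14 + 168 + 30 = 212 |
| Same, visit at the late end of its window | 107 | 219 |
| Of these, nominal dosing days | 56 | 168 |
| Scheduled blood draws | 7 | 11 |
| Pregnancy tests required after baseline, as written | 0 | 0 |
| Tests added by the fix | 3 | 7 |

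**4. Gaps with the fix.** Between week 1 tests: 28 days, or 28 + 3 + 3 = 34 with visit windows. From the last week 1 test to the post-treatment test: 28 + 30 = 58 days, or 28 + 3 + 30 + 7 = 68 with windows.

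**5. Where the 30-day visit falls.** 274/24 = 11.4 days and 296/24 = 12.3 days per half-life. Thirty days is therefore 30/12.3 = 2.4 to 30/11.4 = 2.6 half-lives after the last dose, so some drug may still be present. The 6-month contraception period, taken as about 180 days, is 180/12.3 = 14.6 to 180/11.4 = 15.8 half-lives.

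**The case against.** The strongest reply is that the plan already has its main control and breaks no rule of its own. Contraception is required throughout treatment and for roughly 15 half-lives afterwards. The sections agree with each other, and the documents set no testing frequency that the plan fails to meet. Few patients may be concerned: there are only 12, all previously treated for recurrent or metastatic disease, and the eligible sites include penis and oropharynx. The 14 days is a maximum, so a day 1 test is already permitted. The fix is also partial. Testing would stop at a visit that may be missed, leaving about five of the six contraception months untested.

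Most of this stands, and it limits the point to an improvement. It does not remove it: contraception can fail, a permitted day 1 test is not a required one, and blood is being drawn anyway.

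Three stronger readings are tempting but not supported.

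- **Longer gaps.** A reader might add a 21-day delay to every cycle and reach 14 + 49 × 2 + 37 = 149 days for two cycles, or 14 + 49 × 6 + 37 = 345 for six. Section 11.2 allows such delays but does not say that they lengthen the cycle. The sum also stacks every maximum. Of the 345 days, 6 × 21 = 126 would be delay and 14 + 37 = 51 would fall before the first dose or after the last, none of them dosing days.
- **Pregnancy is nowhere addressed.** Item 8 is an entry rule that names it. Only stopping and reporting rules do not.
- **Dosing would continue after a known pregnancy.** Sections 11.2 and 13.0 give the investigator ample room to interrupt treatment or remove the patient, and Section 17.3 covers a resulting birth defect. The absence of a mandatory rule does not show that a known pregnancy would be ignored. The consent pages are not available, so instructions there cannot be checked.

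**Conclusion.** The point holds as a low-cost safety improvement. One baseline test, up to 14 days before therapy, is the only scheduled check for pregnancy during open-ended dosing of a possible teratogen. On the nominal schedule up to 100 days (two cycles) or 212 days (six cycles) pass between that test and the 30-day visit, with no test required there either. Both figures assume the test is done on the earliest permitted day, cycles run without delay and treatment ends at the end of a cycle.

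They measure calendar time without a test and say nothing about the probability of pregnancy or harm. The documents do not give the number of patients of childbearing potential, so no risk can be calculated. The lack of a stopping or reporting rule that names pregnancy is worth tidying up, but is not a separate ground for the finding.

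**What to change.** For patients of childbearing potential, extend the pregnancy test row in the Section 10.0 calendar to:

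- Cycle 1 week 1, with the result known before the first dose, unless the baseline test was done that same day;
- week 1 of each later cycle;
- the 30-day post-treatment visit, if attended.

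All tests use serum from draws already scheduled. The contraception requirement stays as it is, and no visit is added.

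Two clarifying sentences should accompany the tests: in Section 13.0, that a confirmed pregnancy stops ribavirin; in Section 17.3, that a pregnancy during treatment or within 6 months of the last dose is reportable when it becomes known.

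The cost is up to k + 1 extra tests for a patient on k cycles (3 for two cycles, 7 for six), with one fewer if the post-treatment visit is missed. The day 1 sample must be drawn early enough for the first dose to wait for its result, and an occasional false positive will need a repeat. In return, the nominal gap between on-treatment tests becomes 28 days (34 with visit windows). The gap to the post-treatment test is about 58 days (up to 68 with windows) when treatment ends at the end of a cycle.

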### 6.3 Subject Exclusion Criteria

1. History of hemolytic anemia or thalassemia
2. Current treatment or known prior treatment with ribavirin
3. Active infection or serious underlying medical condition that would impair the patient's ability to receive protocol treatment.
4. Current therapeutic anticoagulation with Coumadin (warfarin)
5. Known brain metastases

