### 12.1.3 Methods for Evaluation of Measurable Disease

## MEMORIAL SLOAN-KETTERING CANCER CENTER

IRB#: 14-211 A (7)

APPROVED: 19 DEC 2016

All measurements should be taken and recorded in metric notation using a ruler or calipers. All baseline evaluations should be performed as closely as possible to the beginning of treatment and never more than 4 weeks prior to registration.

The same method of assessment and the same technique should be used to characterize each identified and reported lesion at baseline and during follow-up. Imaging-based evaluation is preferred to evaluation by clinical examination unless the lesion(s) being followed cannot be imaged but are assessable by clinical exam.

Clinical lesions Clinical lesions will only be considered measurable when they are superficial (e.g., skin nodules and palpable lymph nodes) and  $\geq 10$  mm diameter as assessed using calipers (e.g., skin nodules). In the case of skin lesions, documentation by color photography, including a ruler to estimate the size of the lesion, is recommended.

Chest x-ray Lesions on chest x-ray are acceptable as measurable lesions when they are clearly defined and surrounded by aerated lung. However, CT is preferable.

Conventional CT and MRI This guideline has defined measurability of lesions on CT scan based on the assumption that CT slice thickness is 5 mm or less. If CT scans have slice thickness greater than 5 mm, the minimum size for a measurable lesion should be twice the slice thickness. MRI is also acceptable in certain situations (e.g. for body scans).

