### 12.1.4 Response Criteria

#### 12.1.4.1 Evaluation of Target Lesions

Complete Response (CR): Disappearance of all target lesions. Any pathological lymph nodes (whether target or non-target) must have reduction in short axis to  $<10$  mm.

Partial Response (PR): At least a 30% decrease in the sum of the diameters of target lesions, taking as reference the baseline sum diameters.

Progressive Disease (PD): At least a 20% increase in the sum of the diameters of target lesions, taking as reference the smallest sum on study (this includes the baseline sum if that is the smallest on study). In addition to the relative increase of 20%, the sum must also demonstrate an absolute increase of at least 5 mm. (Note: the appearance of one or more new lesions is also considered progressions).

Stable Disease (SD): Neither sufficient shrinkage to qualify for PR nor sufficient increase to qualify for PD, taking as reference the smallest sum diameters while on study.

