### 14.0 BIOSTATISTICS

A sample size of 12 patients will be accrued and followed until progression of disease (or until removal of study for other medical/logistical reasons), in this pilot study with the objective to obtain preliminary evidence of efficacy in the selected patient population of R/M HPV related malignancies. Radiographic responses, determined by RECIST 1.1 criteria, will be tabulated by adding partial responses and complete responses (CR + PR). The best response for each patient during the study will be used.

Efficacy considerations for the statistical design of this study are informed by historical data regarding second-line or greater systemic therapy for patients with recurrent/metastatic (R/M) head and neck cancer, cervical cancer, or anal cancer. Among patients with R/M head and neck cancer, the historical estimate for objective response rate with palliative chemotherapy after first line is 15% [39, 40]. Similarly, the response rate of palliative single agent chemotherapy for advanced cervical cancer is approximately 15-20% [41, 42]. For R/M anal cancer, no regimen has been shown to be effective after first line platinum + 5-fluorouracil [43].

The regimen would be considered worthy of further study if radiographic responses are observed in at least 2 of 12 subjects. The probability of missing an effect (observing 0 or 1 responses out of 12 patients if the true response rate is 30%), is 0.09. Overall Survival and Progression-Free Survival will be estimated with the Kaplan-Meier method.

Tissue correlative studies will be for purposes of hypothesis generation. We will explore if the anti-Gli-1 IHC score (scale 0-3 dichotomized to low/high) is related to response (CR+PR) using Chi-square or Fisher's exact test. The following provisional scoring system will be used (% refers to percentage of tumor cells that stain positively [cytoplasm and/or nucleus] for Gli 1):

IHC score 0: <=5%

IHC score 1: >5 and <=30%

IHC score 2: >30% and <=50%

IHC score 3: >50%

Additionally, baseline and post-progression Gli-1 expression will be reported (using this provisional scoring system) among the patients who have an initial radiographic response and a post-progression biopsy.

The number and grade of toxicities will be tabulated using NCI CTCAE version 4, as well as the number of dose reductions in all cycles.

The projected accrual rate is 1 to 2 patients per month.

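### Entry requires a prior systemic regimen, but no interval since its last dose and no baseline scan after that dose, so carried-over shrinkage could be counted as a ribavirin response

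*Combined protocol and SAP*

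**What the plan says.** **Eligibility.** Section 6.2 admits "Recurrent and/or metastatic HPV-related carcinoma of the cervix, anus, vagina, vulva, penis, or oropharynx" (item 1), asks for "Measurable disease according to RECIST 1.1 criteria" (item 4), and requires "At least one prior systemic therapy regimen for R/M HPV-related carcinoma" (item 9). Section 6.3 lists five exclusions. Only two concern drugs: "Current treatment or known prior treatment with ribavirin" and current warfarin. None of the nine inclusion or five exclusion criteria mentions the time since the last dose of the prior regimen, or whether the cancer progressed on or after it.

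**Baseline scan.** Section 8.1 asks for "Baseline cross-sectional imaging of the known sites of disease (CT or MR) within 4 weeks prior to therapy", and footnote b of the Section 10.0 schedule repeats that window. Section 12.1.3 wants baseline evaluations as near to the start of treatment as possible and "never more than 4 weeks prior to registration". None of these refers to the last dose of the prior regimen.

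**Scoring.** Under Section 12.1.4.1 a partial response is "At least a 30% decrease in the sum of the diameters of target lesions, taking as reference the baseline sum diameters". Section 12.1.4.3 makes best response depend on confirmation as well as measurement. Its table for measurable disease asks for confirmation at 4 weeks or later in non-randomized trials whose primary endpoint is response.

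**Decision.** Section 14.0 adds complete and partial responses and states: "The best response for each patient during the study will be used". At least 2 responders among 12 make the regimen worth pursuing. Section 4.2 confirms that there is no randomization.

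**The concern.** Every patient arrives from an earlier systemic regimen. With no comparator, only the entry rules and the timing of the baseline scan separate a ribavirin effect from the tail of that regimen. As written, a patient could be scanned, receive a last dose of the earlier drug, and start ribavirin within the 4-week window. Part of any later fall in the sum of diameters would then belong to the earlier drug. Describing ribavirin as monotherapy rules out concurrent treatment, but not residual effect from treatment just stopped.

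At stake is the primary objective. One misattributed response is half of the 2-of-12 threshold, and two would meet it with no ribavirin effect at all. Secondary objective 2 is also touched. Section 14.0 tabulates toxicities by number and grade without mentioning attribution, so lingering toxicity of the earlier regimen could enter the ribavirin safety table.

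**Working it through.** **1. The plan's own figure.** Inputs from Section 14.0: n = 12, threshold 2, true rate 30%, stated probability of missing the effect 0.09.

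P(0 or 1 response) = 0.70^12 + 12 × 0.30 × 0.70^11 = 0.0138 + 0.0712 = 0.085, which rounds to 0.09. The figure is reproduced, and nothing below changes it.

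**2. Timing.** The baseline scan may be up to 4 weeks before Day 1. Section 9.1 places the first on-study scan in the last week of cycle 2: 2 × 28 days, or about week 8. Up to about 4 + 8 = 12 weeks can separate the two scans, of which up to 4 precede any ribavirin. The next scheduled scan is at the end of cycle 4, about week 16, which would satisfy a 4-week confirmation.

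**3. What carry-over must do to count.** It must amount to a decrease of at least 30% from baseline by an on-study scan, with no new lesions, and still be present at confirmation. That removes transient shrinkage. It does not remove a durable response to the earlier regimen, because confirmation tests persistence, not cause.

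**4. Size with one carry-over patient.** The documents give no frequency, so let q be an assumed probability that the trial contains one patient whose carry-over is scored as a response. Let p be the true ribavirin response rate.

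- No carry-over: G0 = 1 − (1−p)^12 − 12p(1−p)^11
- One certain carry-over, so one more response is needed among 11: G1 = 1 − (1−p)^11
- Mixture: (1−q) × G0 + q × G1

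At p = 5%, G0 = 1 − 0.5404 − 0.3413 = 0.118 and G1 = 1 − 0.5688 = 0.431.

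- q = 10%: 0.9 × 0.1184 + 0.1 × 0.4312 = 0.150
- q = 25%: 0.75 × 0.1184 + 0.25 × 0.4312 = 0.197

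| True rate p | No carry-over | q = 10% | q = 25% | One certain |
|---|---|---|---|---|
| 5% | 0.118 | 0.150 | 0.197 | 0.431 |
| 10% | 0.341 | 0.376 | 0.427 | 0.686 |
| 15% | 0.557 | 0.584 | 0.626 | 0.833 |

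The 15% row is the historical head and neck rate quoted in Section 14.0.

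**5. Carry-over spread over several patients.** Suppose instead that 4 of the 12 enter soon after a prior regimen, each with an independent carry-over probability c. Each of those 4 then has response probability 1 − (1−p)(1−c), and the other 8 have p. The chance of at least 2 responses is:

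| True rate p | c = 5% | c = 20% |
|---|---|---|
| 0% | 0.014 | 0.181 |
| 5% | 0.184 | 0.406 |
| 15% | 0.610 | 0.750 |

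Both the 4 patients and c are assumptions.

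**The case against.** The plan has real safeguards. A reader might infer that any shrinkage after the baseline scan is scored as a response. The documents do not support that: the fall must reach 30%, and the confirmation rule appears to apply because this is a non-randomized trial judged on response. Section 12.1.3 also asks for baseline evaluations close to the start of treatment, which works against a scan followed by another dose of the old drug. These points narrow the route. They do not close it, since neither orders the scan after the last prior dose and confirmation cannot identify cause.

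A reader might also see a conflict between the windows in Sections 8.1 and 12.1.3. There is none. Both are upper limits, and when registration precedes Day 1, a scan within 4 weeks before therapy is also within 4 weeks before registration.

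It is tempting to say that the entry rule must demand progression, because the benchmark describes treatment after first line. Section 14.0 does not say that the historical patients had all failed earlier therapy, and the entry rules of those series are not given. Mandatory progression would exclude patients who stopped the earlier regimen for intolerance, a group that Section 6.2 leaves eligible. That is a choice of population.

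Finally, the largest increases assume that one carry-over response is certain. This objection stands: those figures are an upper case for a single patient, not an expectation.

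**Conclusion.** The gap holds on the text: there is no minimum interval since the prior regimen and no requirement that the baseline scan follow its last dose. Persistent shrinkage of at least 30% from the earlier regimen could therefore count toward the 2-of-12 rule.

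The size is conditional. At a true rate of 5%, the chance of meeting the rule rises from 0.118 to about 0.15 or 0.20 if there is a 10% or 25% chance that the trial contains one carry-over responder, and to 0.43 if one is certain. At 15% it rises from 0.557 to 0.833 if one is certain. These figures assume independent responses and a carry-over that survives confirmation. The documents do not show that carry-over is frequent, so it would be wrong to conclude that the decision rule is invalid or that a favourable result must be spurious.

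On safety, residual toxicity could be tabulated under ribavirin. The 14-day baseline history and laboratory tests (Section 8.1) and the entry organ-function limits (Section 6.2) restrict this without excluding it.

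Confidence is high for the gap and its mechanism, and low for how often it would matter. It is a worthwhile, inexpensive improvement.

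**What to change.** In Sections 6.2 and 8.1:

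- Require that the baseline RECIST scan be obtained after the last dose of the most recent anticancer therapy, within the existing 4-week window.
- Require a minimum interval between that last dose and Day 1, its length set by the sponsor. This is needed as well, because a scan after the last dose does not by itself exclude delayed shrinkage.

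In data collection and reporting:

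- Record for each patient the date of the last prior dose and whether disease had progressed on or after that regimen.
- Report each responder with this information, so that a reader can judge attribution.

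Making progression an entry condition is optional for the sponsor.

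The cost is a few lines of amendment text and two data items. A few patients would wait or have their baseline scan re-timed. The sample size, the 2-of-12 rule and the stated 0.09 stay as they are.
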